4. ANALYSIS SETS AND TREATMENT GROUPS

4.1. Analysis Sets (Part A)

4.1.1. Intent-to-Treat Set (Part A)

The ITT Set will be defined as all subjects randomized. A subject's randomized treatment sequence will be used for analysis regardless of the actual treatment received. ITT Set will be used for disposition and demographic analysis.

4.1.2. Safety Set (Part A)

The Safety Set will be defined as all subjects who received at least one dose of the IMP (KLS-GABA or KLS). The actual treatment received will be used for analysis according to treatment period. Safety Set will be used for all safety analyses and endpoints.

4.1.3. Pharmacokinetic Set (Part A)

The PK Set will be defined as all subjects who received at least one dose of the IMP (KLS-GABA or KLS) and have evaluable PK data. The actual treatment received will be used for analysis according to treatment period. PK Set will be used for all PK analyses and endpoints.

4.2. Analysis Sets (Part B)

4.2.1. Intent-to-Treat Set (Part B)

The ITT Set will be defined as all subjects randomized. A subject's randomized treatment will be used for analysis regardless of the actual treatment received. ITT Set will be used for disposition and demographic analysis.

4.2.2. Safety Set (Part B)

The Safety Set will be defined as all subjects who received at least one dose of the IMP (KLS, KLS-GABA, gabapentin, or Placebo). The actual treatment received will be used for analysis. Safety Set will be used for all safety analyses and endpoints.

4.2.3. Pharmacokinetic Set (Part B)

The PK Set will be defined as all subjects who received at least one dose of the IMP (KLS, KLS-GABA, gabapentin, or Placebo) and have evaluable PK data. The actual treatment received will be used for analysis. PK Set will be used for all PK analyses and endpoints.

4.2.4. Pharmacodynamic Set (Part B)

The PD Set will be defined as all randomised subjects who received a dose of randomised therapy and complete the ID capsaicin injection. The actual treatment received will be used for analysis. The analyses of efficacy endpoints will use the PD set.

Statistical Analysis Plan

4.3. Treatment groups

For summary statistics, subjects will be presented in different ways, as applicable:

- for Part A:
 - by planned treatment sequence of randomized subjects ("[KLS 80 mg - GABA 34 mg] – KLS 80 mg" and "KLS 80 mg – [KLS 80 mg - GABA 34 mg]"). This presentation will be used optionally for descriptive outputs (disposition, demographics, etc.), but generally will not be used for analysis of endpoints.
 - by actual treatment of subjects in each treatment period ("KLS 80 mg - GABA 34 mg" and "KLS 80 mg"). This presentation will be used for analysis of endpoints, and optionally for descriptive outputs (disposition, demographics, etc.).
- for Part B:
 - by planned treatment of subjects ("KLS 40 mg", "KLS 80 mg", "KLS 160 mg", "KLS 40 mg - GABA 17 mg", "KLS 80 mg - GABA 34 mg", "KLS 160 mg – GABA 68 mg", "Gabapentin 300 mg", "Placebo"). This presentation will be used for descriptive outputs (disposition, demographics, etc.).
 - by actual treatment of subjects ("KLS 40 mg", "KLS 80 mg", "KLS 160 mg", "KLS 40 mg - GABA 17 mg", "KLS 80 mg - GABA 34 mg", "KLS 160 mg – GABA 68 mg", "Gabapentin 300 mg", "Placebo"). This presentation will be used for analysis of safety, efficacy and PK endpoints.

Statistical Analysis Plan

5. ANALYSIS PERIODS

There will be two treatment periods within Part A. Analysis phases and treatment periods:

- SCREENING analysis phase starts with sign of Informed Consent and ends with first IMP administration;
- TREATMENT PERIOD 1 analysis phase/period starts with first IMP administration within Part A and ends with second IMP administration within Part A;
- TREATMENT PERIOD 2 analysis phase/period starts with second IMP administration within Part A and ends with the end of study.

There will be one treatment period within Part B. Analysis phases and treatment periods:

- SCREENING analysis phase starts with sign of Informed Consent and ends with first IMP administration;
- TREATMENT PERIOD analysis phase/period starts first study drug administration and ends with the end of study.

Statistical Analysis Plan

6. ANALYSIS METHODS

6.1. Participant Disposition

Disposition will be summarized descriptively using counts and percentages for All Patients separately for Part A and Part B. Subjects from Part A will be analysed by planned treatment sequence and overall. Subjects in the Part B will be analysed by planned treatment and in overall. The number and percentage of subjects entered into the study, enrolled in the study, randomized, and treated as well as number and percentage of subjects completed the study will be presented, together with number and percentage of subjects who prematurely discontinued from the study along with reasons for study discontinuation.

A listing of subject disposition status will be provided separately for Part A and Part B. The number of subjects in each analysis set will be summarized descriptively by treatment with counts and percentages separately Part A and Part B.

A listing of subject's inclusion to analysis sets will be provided separately for Part A and Part B. A subject's eligibility with inclusion/exclusion criteria completions or violations will be listed separately for Part A and Part B.

6.2. Protocol Deviations

The frequency and percentage of participants in each protocol deviation category will be summarised using the Safety Set. Participants from Part A will be analysed by planned treatment sequence and overall and by actual treatment during the study and overall. Participants in the Part B will be analysed by actual treatment and in overall.

All protocol deviations will be listed using the Safety Set.

6.3. Demographic and Baseline Characteristics

Demographic data and baseline characteristics, including age, gender, ethnicity, height, body weight and BMI will be summarised.

Demographic data will include gender, age and ethnicity. Baseline characteristics will include body weight, height and BMI.

Demographics and baseline characteristics will be summarized for all subjects overall and by treatment sequence (Part A) or treatment (Part B). Summary statistics will be generated for all continuous variables (i.e., age and weight, height and BMI) and the number and percentage of subjects within each category will be presented for all categorical variables (i.e., gender, race and ethnicity). The summary results for Part A and Part B will be based on the ITT Set.

6.4. Medical History

Medical history will be coded using Medical Dictionary for Regulatory Activities (MedDRA) of latest version (version will be clarified in the output footnotes), listed and summarized with descriptive statistics by System Organ Class (SOC) and Preferred Term (PT) separately for Part A (by treatment sequence based on ITT Set) and for Part B (by treatment based on ITT Set).

Statistical Analysis Plan

6.5. Prior and Concomitant Medication

Medications will be coded with the latest version of the WHO drug dictionary, listed and presented by ATC Class 2 and Preferred Term. Each medication will be classified as prior or concomitant.

Prior medication will be defined as any medication that was stopped prior to the start of taking the study drug/ taken during the 30-day period before signing the ICF. Prior medications will be summarised based on ITT Set by treatment sequence and overall for Part A and based on Safety Set by treatment and overall for Part B.

Concomitant medication will be defined as any ongoing medication used at the time of the start of taking the study drug /all medications taken after the study drug administration. Concomitant medications will be summarised based on Safety Set by treatment according to treatment period and overall. If the medication was ongoing during both treatment periods in Part A then it will be considered as concomitant for both treatments.

6.6. Safety Parameters

Unless specified in any of the further sections, analysis of Safety parameters will be based on Safety Set.

6.6.1. Adverse Events (AE)

All verbatim AE terms will be coded using MedDRA of latest version (version will be clarified in the output footnotes) and summarized by system organ class (SOC) and preferred term (PT).

A TEAE will be defined as any AE that has an onset on or after taking study drug, or any pre-existing condition that has worsened on or after taking study drug. For Part A each TEAE will be attributed to treatment period and treatment according to onset date.

The frequency and incidence of TEAEs will be summarised by SOC and PT by treatment according to treatment period and overall. Summaries will also include, but not limited to, relationship to study drug and maximum severity. The summary will be sorted by SOC and PT by frequency from the highest to the lowest. All AE data will be listed.

For each of the summaries produced at the participant level, multiple occurrences of the same event within a participant will be counted once in the summaries by SOC and PT; multiple occurrences of the same event within a participant will be counted once in the maximum severity category and/or maximum drug relationship category. If severity or relationship is found to be missing, the most severe occurrence will be imputed for that particular summary.

These summaries will also present the number of events that occurred, so multiple occurrences of the same event within a participant will all be accounted for in the maximum intensity category and maximum relationship category they were classed as.

6.6.2. 12-lead electrocardiogram (ECG)

Descriptive statistics will be calculated for absolute value and change from baseline (pre-dose) of each parameter by visit and by treatment according to treatment period and overall. Where multiple values are recorded at a timepoint for a subject, the mean of the values will be used in the summary statistics.

Statistical Analysis Plan

6.6.3. Vital signs

Vital signs will include systolic blood pressure, diastolic blood pressure, body temperature and heart rate. Descriptive statistics will be calculated for absolute value and change from baseline (pre-dose) of each parameter by visit, by timepoint and by treatment according to treatment period. Frequency tabulations of the abnormalities will be provided for each parameter by visit, by timepoint (including only timepoints with PI Interpretation) and by treatment according to treatment period and overall.

6.6.4. Clinical laboratory

Clinical Laboratory evaluation results (haematology and blood chemistry) will be summarised. Descriptive statistics will be calculated for absolute value and change from baseline (pre-dose) of each parameter by visit and by treatment according to treatment period. Categorical parameters (if applicable) will be summarised by counts and percentages of participants within each category by treatment group and visit. All presentations will be based on the International System of Units. The frequency of laboratory abnormalities will be tabulated.

Urinalysis data will be listed only. Clinical Laboratory listings will flag values that are outside normal reference ranges or markedly abnormal findings.

6.6.5. Physical Examination

Physical examination data will be summarised separately for Part A (by treatment sequence based on ITT Set) and for Part B (by treatment based on Safety Set).

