10.5.2.5. Physical Examination

Physical examination data will be listed for individual subjects. Summary statistics will be calculated for each parameter by treatment and time.

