1.1.2. Secondary Objectives (Part A)

The secondary objective of the Part A is:

- To determine the safety and tolerability of a single oral dose of KLS-GABA (80 mg-34 mg) compared to KLS alone (80 mg) in healthy male subjects.

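### SAP 6.6.5 summarises Part A physical examinations by randomised sequence in the ITT Set with no visit or period, so the planned table does not present findings by KLS-GABA versus KLS; the conflict is undeclared but the impact is modest.

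*SAP*

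**What the plan says.** SAP 6.6.5 gives this rule: "Physical examination data will be summarised separately for Part A (by treatment sequence based on ITT Set". The same sentence uses treatment and the Safety Set for Part B. Neither half names a visit, timepoint or period.

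Other parts of the plan point elsewhere for Part A:

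- SAP 4.1.2, on the Safety Set: "The actual treatment received will be used for analysis according to treatment period. Safety Set will be used for all safety analyses and endpoints".
- SAP 4.1.1, on the ITT Set: "A subject's randomized treatment sequence will be used for analysis regardless of the actual treatment received". Its stated use is narrow: "ITT Set will be used for disposition and demographic analysis".
- SAP 4.3 offers the sequence presentation for descriptive outputs, "but generally will not be used for analysis of endpoints". Endpoints go by actual treatment in each period.
- Protocol 10.5.2.5 promises an individual listing and also a summary: "Summary statistics will be calculated for each parameter by treatment and time".

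SAP 1.2.2 names physical examination within the Part A secondary endpoint. The matching objective in SAP 1.1.2 is comparative: "To determine the safety and tolerability of a single oral dose of KLS-GABA (80 mg-34 mg) compared to KLS alone (80 mg"). SAP 8 lists one change from the protocol, the Part B primary endpoint.

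**The concern.** In a two-period crossover, a sequence label describes the order of the drugs, not the drug. Each planned Part A sequence contains both KLS-GABA and KLS. A summary whose only stated classification is sequence therefore does not show which drug preceded a finding, and that is what the safety objective asks.

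SAP 6.6.1 to 6.6.4 summarise adverse events, ECG, vital signs, haematology and chemistry by treatment according to period. SAP 6.6.5 departs from that pattern without a reason and without an entry in SAP 8. At stake is whether one component of the secondary safety endpoint is tabulated in a form that answers its own objective, and whether a programmer can tell from the SAP which examination belongs to which drug.

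**Working it through.** The documents give no figure to reproduce. The check has three steps.

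**1. The rules side by side (Part A)**

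| Source | Set | Classification | Visit or time |
|---|---|---|---|
| SAP 6.6.5 | ITT | Randomised sequence | Not stated |
| SAP 4.1.2 | Safety, for all safety analyses | Actual treatment by period | Not stated |
| SAP 4.3 | Not stated | Actual treatment by period for endpoints | By period |
| SAP 6.6.2 to 6.6.4 | Safety (default in SAP 6.6) | Treatment by period | By visit |
| Protocol 10.5.2.5 | Not stated | Treatment | By time |

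SAP 6.6.5 differs from the others on classification. It differs on set from those that name one, and it omits the visit that its neighbours give.

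**2. Which examinations exist**

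Protocol Appendix 1 schedules physical examination at Screening, at Day -1 of each period and at the Post-Study visit, with none on Days 1 to 3.

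- Per subject: 1 + 2 + 1 = 4 examinations.
- After a dose: 2 of the 4, namely Period 2 Day -1 and Post-Study.
- For 12 subjects: 12 × 2 = 24 post-dose examinations at most.

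SAP 5 runs analysis Period 1 up to the second dose, so Period 2 Day -1 falls in Period 1 and Post-Study in Period 2. SAP 3 makes Period 2 Day -1 the Period 2 baseline and limits Part A change from baseline to Days 1 to 3. Under that limit, 0 physical examinations qualify in either period.

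**3. What a by-sequence table can show**

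Let p1 be the chance of a finding at the examination that follows KLS-GABA, and p2 at the one that follows KLS. Assume no period or carryover effect and that both periods are completed.

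| Sequence | Period 2 Day -1 | Post-Study | Sum over both visits |
|---|---|---|---|
| KLS-GABA then KLS | p1 | p2 | p1 + p2 |
| KLS then KLS-GABA | p2 | p1 | p2 + p1 |
| Difference | p1 - p2 | p2 - p1 | 0 |

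Pooled over visits, the expected difference per completing subject is (p1 + p2) - (p2 + p1) = 0, whatever the value of p1 - p2. Split by visit, the difference is p1 - p2 at one visit and p2 - p1 at the other, so the drug comparison can be recovered. The outcome therefore turns on the visit layout, which SAP 6.6.5 leaves open.

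**The case against.** The strongest reply is that this is a wording inconsistency with little consequence. Its parts, and what stands of each:

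- **Pooling over visits is not stated.** This stands. The neighbouring sections work by visit, the protocol says by time, and SAP 9 puts the shells in a separate document. A reader might infer that the contrast is always zero, or that the drugs cannot be compared. The documents do not support that: sequence plus visit identifies the preceding planned drug.
- **Findings are attributed elsewhere.** This largely stands. Under Protocol 7.5.1.1 and 7.5.1.5, new or worsened signs and clinically significant abnormal assessments become adverse events, and SAP 6.6.1 assigns each Part A treatment-emergent event to a period and treatment. All examination data are also listed. A claim that findings are never attributed to a drug would therefore be wrong. Findings not judged clinically significant may still appear only in the listings and this summary.
- **SAP 6.6 allows exceptions to the Safety Set.** It does, and SAP 4.3 is qualified by the word generally. That permits a different set. It does not reconcile SAP 6.6.5 with Protocol 10.5.2.5 or with a comparative objective.
- **The ITT label may change nothing.** A reader might infer that undosed subjects enter the table. Protocol 11.1 keeps subjects who consented but were not dosed out of the database, so read literally they contribute no examinations. Dosing is directly observed (Protocol 5.4), so randomised and actual treatment part only after a dosing error.
- **Physical examination is not alone.** Correct. SAP 6.6.4 lists urinalysis without summarising it, and its summary does not name coagulation. Both belong to the same endpoint. It would be wrong to call physical examination the only component without a by-treatment summary.

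**Conclusion.** The point holds in a limited form. The Part A rule in SAP 6.6.5 conflicts with SAP 4.1.2, with the stated uses in SAP 4.1.1 and 4.3, and with Protocol 10.5.2.5, and SAP 8 does not declare the departure. As written, the planned summary does not present examination findings by KLS-GABA versus KLS.

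The further statement, that the between-sequence contrast is uninformative about the drug difference, is conditional. It needs visits pooled within sequence and no period or carryover effect.

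The size is modest. The issue concerns at most 24 post-dose examinations in 12 subjects, within a descriptive secondary safety endpoint for which SAP 3 rules out hypothesis testing, and findings remain traceable by other routes. The correction is worth making because it is nearly free and makes the planned table answer the stated objective.

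**What to change.** - **SAP 6.6.5:** for Part A, summarise *by actual treatment according to treatment period and by visit, Safety Set*.
- **Assignment of visits:** state that the Period 2 Day -1 examination is the post-dose examination for the Period 1 treatment (in line with SAP 5) and also the Period 2 baseline (in line with SAP 3). State that the Post-Study examination belongs to the Period 2 treatment.
- **SAP 3:** exempt physical examination from the Days 1 to 3 limit on change from baseline, since Appendix 1 schedules none on those days. The same sentence refers to an unfilled Section X, which can be completed at the same time.
- **If the sequence layout is kept:** split it by visit, and declare and justify the departure from Protocol 10.5.2.5 in SAP 8.

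The cost is a few sentences in the SAP and one revised table shell, with no new data. The limitation that remains is timing. Period 2 Day -1 follows a washout of at least 7 days and Post-Study comes 5 to 7 days after the final dose, so the comparison is still a late one, about a week after each dose. One examination also serves both as a Period 1 outcome and as the Period 2 baseline.

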6.7. Pharmacokinetic Analysis

The PK analysis is outside the scope of this analysis plan. That analysis will be described in a separate document.

6.8. Pharmacodynamic Analysis

PD analysis will be conducted for Part B only and will be based on Pharmacodynamic Set.

6.8.1. Descriptive PD analysis

Descriptive statistics will be calculated for absolute value and change from baseline (with baseline defined as the day -1 observation at each post-Capsaicin injection timepoint) for Scores (VAS or NRS) and Area measured (cm²) by visit and by treatment according to treatment period.

The list of PD parameters includes:

- area of hyperalgesia (Primary Endpoint);
- measurement of pain score;
- pain score of hyperalgesia;
- area of allodynia;

Statistical Analysis Plan

- pain score of allodynia;
- area of flare.

6.8.2. PD Figures

Corresponding figures will be produced for each PD parameter (see [Section 6.8.1](#)):

- individual PD figures by timepoint separately for each patient.
- PD figures by treatment group (individual and combined – see below) and timepoint with the overall mean (\pm Standard Error) across patients.

6.8.3. PD Modelling

Two separate sets models will be fit to the data. Individual models will be fit per treatment group ("KLS 40 mg", "KLS 80 mg", "KLS 160 mg", "KLS 40 mg - GABA 17 mg", "KLS 80 mg - GABA 34 mg", "KLS 160 mg – GABA 68 mg", "Gabapentin 300 mg", "Placebo") to assess means and change from baseline in score and area for each PD parameter (see [Section 6.8.1](#)). Combined models will be fit using combined treatments (i.e. different doses of the same treatment combined – "KLS alone", "KLS-GABA", "Gabapentin", "Placebo") to assess differences in means and change from baseline in score and area for each PD parameter (see [Section 6.8.1](#)).

Individual models (by treatment):

The MMRM model will contain terms for the actual treatment group (and timepoint and will contain baseline Score / Area as a covariate and subject as a random effect.

An unstructured covariance matrix will be assumed. If the fit of the unstructured covariance structure fails to converge, the following covariance structures will be tried in order until convergence is reached: toeplitz with heterogeneity, autoregressive with heterogeneity, toeplitz, and autoregressive.

Least squares (LS) means will be reported by timepoint along with corresponding 95% confidence intervals (CIs).

The model will be fit separately for each treatment group, for the following dependent variables:

- Score / Area for each PD parameter
- Change in score / Area for each PD parameter

Combined models (treatment as a term; comparing against placebo):

The MMRM model will contain terms for actual combined treatment group and timepoint and will contain baseline Score / Area as a covariate and subject as a random effect.

An unstructured covariance matrix will be assumed. If the fit of the unstructured covariance structure fails to converge, the following covariance structures will be tried in order until convergence is reached: toeplitz with heterogeneity, autoregressive with heterogeneity, toeplitz, and autoregressive.

LS means will be reported by timepoint for each treatment group; the difference in LS means between each dose arm and placebo will be presented along with corresponding 95% CIs.

The modelling will be conducted separately for the following dependent variables:

Statistical Analysis Plan

- Score / Area for each PD parameter
- Change in score / Area for each PD parameter

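### The SAP's only model for comparison with placebo pools the three doses of KLS and of KLS-GABA, so it cannot give six of the seven dose-arm differences it promises, and Section 8 does not list the pooling

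*SAP*

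**What the plan says.** SAP 6.8.3 describes two sets of mixed models for the Part B pharmacodynamic (PD) endpoints.

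- **Individual models.** "The model will be fit separately for each treatment group, for the following dependent variables". The output is limited to means: "Least squares (LS) means will be reported by timepoint along with corresponding 95% confidence intervals (CIs". The paragraph nevertheless lists a treatment term: "The MMRM model will contain terms for the actual treatment group (and timepoint".
- **Combined models.** The opening paragraph defines them: "Combined models will be fit using combined treatments (i.e. different doses of the same treatment combined". The heading reads "Combined models (treatment as a term; comparing against placebo". The factor is pooled over dose: "The MMRM model will contain terms for actual combined treatment group and timepoint". The promised output is not pooled: "the difference in LS means between each dose arm and placebo will be presented along with corresponding 95% CIs".

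Protocol 10.5.4.2 (Model Group 2) fits all treatment groups together, with randomised treatment group as the term, and reports each dose arm against placebo. Nothing there merges doses. SAP 4.3 lists only the eight individual arms for Part B and says of the by-actual-treatment version: "This presentation will be used for analysis of safety, efficacy and PK endpoints". SAP Section 8 records one departure from the protocol, the change of the Part B primary endpoint to area of hyperalgesia.

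**The concern.** Within one block of SAP 6.8.3, the stated factor cannot produce most of the stated output. The output sentence makes sense beside the protocol's unpooled factor. It stops making sense once the doses are merged.

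SAP Section 3 rules out hypothesis testing, so estimates and confidence intervals are the inferential output. As written, no specified model gives a placebo-adjusted estimate with an interval for any single dose of KLS-GABA or KLS, including on the SAP's primary endpoint. A programmer must follow either the factor or the output sentence. If that choice is made after unblinding, it depends on the data. It also affects the answer, because a pooled difference equals the effect at each dose only if the dose response is flat.

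**Working it through.** The plan has no power figure to reproduce: Protocol 10.2 reports no formal sample size calculation, and neither document gives an SD. The allocation is consistent: 128 subjects / 8 treatments = 16 per arm, and 8 blocks of 16 = 128.

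**1. What the pooled factor can estimate.** With 16 per arm, the KLS-alone contrast weights the arm means 1/3, 1/3, 1/3 (40, 80, 160 mg) against −1 for placebo, whichever dose is asked for. KLS-GABA behaves the same way. Gabapentin has weight 1 on its own arm. So 4 − 1 = 3 distinct differences exist, and 1 of the 7 arm differences is recovered. An eight-level factor gives 8 − 1 = 7. This step needs no SD.

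**2. What the individual models add.** Each is fitted to one arm. A treatment term is constant there and cannot be estimated, and no placebo subjects are in an active-arm fit. No placebo difference is promised from these fits.

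**3. What the pooled estimate measures.** Assume an effect of 1 SD at 160 mg.

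| Assumed dose response (40, 80, 160 mg) | Pooled difference |
|---|---|
| Top dose only: mean(0, 0, 1) | 0.33 SD |
| Linear through zero: mean(0.25, 0.5, 1) | 0.58 SD |
| Flat: mean(1, 1, 1) | 1.0 SD |

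**4. Precision, in residual SD units with the SD held fixed.** SE = sqrt(1/n1 + 1/n2), and the 95% half-width is t × SE. Residual df allow for one baseline covariate: 128 − 4 − 1 = 123 and 128 − 8 − 1 = 119. At one timepoint:

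- pooled, 48 v 16: SE 0.2887, half-width 0.571;
- one dose, 16 v 16: SE 0.3536, half-width 0.700;
- ratio of SEs: 0.3536 / 0.2887 = 1.22.

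For a difference held constant over the five post-capsaicin timepoints, assuming compound symmetry with correlation ρ, multiply by sqrt((1 + 4ρ)/5):

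| ρ | Pooled | One dose |
|---|---|---|
| 0.3 | 0.38 | 0.46 |
| 0.5 | 0.44 | 0.54 |
| 0.7 | 0.50 | 0.61 |
| 0.9 | 0.55 | 0.67 |

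**5. Pooled contrast from the eight-level model.** Equal weights on the three doses give 0.57 SD at one timepoint and 0.38 to 0.55 SD averaged over time, the same as the four-level model. If doses differ, the four-level model can do worse, because the differences enter its residual. With a 1 SD effect at the top dose only, each pooled group adds 16 × (1/9 + 1/9 + 4/9) = 10.67 to the residual sum of squares. If this holds for both KLS and KLS-GABA, the SD rises by sqrt((123 + 21.33)/123) = 1.083 and the half-width goes from 0.571 to 0.619. If it holds for KLS-GABA only, the factor is sqrt((123 + 10.67)/123) = 1.04 and the half-width is about 0.60.

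**6. A separate gap: time.** Neither document lists a treatment-by-timepoint term, although Protocol 10.5.4 wants treatment differences at each timepoint and the SAP reports means by timepoint. The term may be intended but unwritten. With only the listed terms, every difference is constant over time. With the interaction, the counts become 3 × 5 = 15 (pooled) and 7 × 5 = 35 (eight-level) per dependent variable.

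**The case against.** The best defence is that pooling may be deliberate and reasonable. This is a Phase I study with no formal sample size and no testing. The Part B objectives do not ask for a placebo contrast at each dose, and pooled KLS-GABA against placebo does address the primary objective. That stands, and it means the eight-level model is not the only valid repair. It does not remove the contradiction: the SAP itself promises the dose-arm differences.

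Dose-level information is not lost. Descriptive summaries, figures with mean and standard error by individual treatment group, and LS means with intervals for all eight arms remain planned. The arms are independent, so an approximate interval could be formed from two separate fits. But the SAP specifies no such subtraction, and each fit has its own baseline slope with no common baseline value. It would not be the promised estimate.

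Three smaller points also have weight. SAP 4.3 opens by referring to summary statistics, so its mismatch with the pooled factor is supporting evidence only. The individual-models paragraph contradicts itself and could be a poorly edited multi-arm model, but even then it promises only means. Table shells are in a separate document not available here; they could show which contrasts are tabulated, but cannot make a pooled factor estimate single doses.

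**Conclusion.** The concern holds and should be fixed. Six of the seven differences promised in SAP 6.8.3 cannot come from the model specified for them, and the departure from Protocol 10.5.4.2 is missing from SAP Section 8. That conclusion is algebra and rests on no assumed SD or effect. What is missing is a pre-specified placebo-adjusted estimate with interval by dose.

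The sizes are illustrative. The 0.33 to 1.0 SD range depends on the assumed dose response. The half-widths assume 16 per arm and a fixed SD, and the time-constant ones also assume compound symmetry, whereas the SAP specifies an unstructured matrix first. The 1.22 ratio depends only on the group sizes.

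**What to change.** In SAP 6.8.3:

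- Fit the between-treatment model with the eight-level treatment factor, timepoint and treatment-by-timepoint, keeping the baseline covariate.
- Report each of the seven active arms minus placebo, with 95% CI, by timepoint.
- Give pooled KLS and pooled KLS-GABA against placebo as equal-weight contrasts from the same model, labelled supportive.
- Remove the treatment term from the models fitted one arm at a time.

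In SAP Section 8, list any pooling that is kept. It would also be tidy to note the move from randomised treatment (Protocol 10.5.4.2) to actual treatment in the model, although Protocol 10.4.3.2 already analyses the PD set by actual treatment.

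If pooling is to remain the main comparison, the minimum repair is to reword the output sentence so that it refers to each combined treatment group, and to list the pooling in Section 8.

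The cost is SAP text and model code, with no extra subjects or data. Per-dose intervals are 1.22 times as wide as pooled ones. Output grows: 6 PD parameters × 2 forms (value and change) = 12 dependent variables, so 12 × 35 = 420 intervals, against 12 × 15 = 180 for a pooled model that also has the interaction. With the SD held fixed, the pooled summary loses no precision.
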